#### **5.3.4 Informed Consent**

The informed consent process will occur either at the Sponsor site or in the comfort of the participant's home, where trained study staff will explain the ICF, study design, participation requirements, and reasonable risks. Participants will be encouraged to ask questions regarding the ICF, study design, and what is being asked of them. The study staff will assess the participants understanding of the entire informed consent, including but not limited to the voluntary nature of study participation, their ability to withdraw from the study at any time, and participation requirements. After signing the ICF, participants will get a copy of the signed ICF for their records.

If the participant is unable to give informed consent, a legally authorized representative (LAR) may sign the ICF, in addition to the participant's verbal assent. Trained study staff will decide whether a LAR may or may not be used.

Participants requiring LARs include but are not limited to participants with mental health disorders, genetic disorders such as Huntington's disease, and neurological conditions such as Alzheimer's disease.

For this study, a legally authorized representative may include:

1. An agent pursuant to an advanced health care directive;
2. A spouse, or
3. A child having the authority to make health care decisions. When possible, the participant will be involved in the informed consent process and provide assent to the best of their ability.

Since Sanguine acts as a Sponsor and as a site, there will be two scenarios for participant consenting and data transfer:

1. As a site, Sanguine will implement a software-as-a-service (SaaS) provider of electronic signature technology and transaction management solutions, so participants electronically sign the ICF and authorize the release of medical records using a tablet or computer from the comfort of their home or through a secure website.
2. Alternatively, if the participant prefers, physical ICFs and information release authorization may be completed using hardcopy documents.

#### **5.3.5 Biospecimen Collection**

Biospecimen collection will occur either at a study-approved clinic, in the comfort of the participant's home, at the participant's workplace (in a private setting), or in other private settings. Participation requires at least one type of tissue collection described below. Biospecimens are collected as a donative gift from the participant to the Sponsor.

##### **5.3.5.1 Blood Collection**

A blood draw is the most common type of biospecimen collection procedure, making up about

95% of biospecimen requests. Blood will generally be collected by venipuncture from a medical professional certified in phlebotomy. Participants may also be asked to provide a microsample of blood via fingerstick. Fingerstick samples will be collected on a blood card, such as a dried blood spot (DBS) card, or into a microtainer. Researchers may use the blood cards for specific testing of biomarkers or isolating genetic material.

Blood collection volumes are dependent on which cohort the participant is placed and self-reported medical data (see Table 1). Blood may be collected every 7 days, but the total volume collected during a 6-week period may not exceed the Table 1 volumes. Maximum blood collection volumes in Table 1 may be collected at one time

**Table 1: Maximum Blood Collection Volume by Cohort**

Cohort	Blood Draw Volume (mL)
Health Condition	≤100mL
Exceptional Condition	≤60mL
Control	≤180mL

The maximum blood collection volume within a 6-week period by cohort.

Participants within the health condition and control groups who weigh less than 110 pounds and/or are older than 85 years old will have a maximum collection volume of 75mL within a 6-week period.

Before the phlebotomy procedure, a Sanguine designated phlebotomist will assess the participants health by asking questions like, “Do you feel healthy today?” and noting any physical symptoms that may require the blood draw to be aborted. The phlebotomist then decides if the blood draw can continue as scheduled. The blood draw appointment follows phlebotomy best practices set forth by the College of American Pathology (CAP) and the World Health Organization (WHO). Venipuncture is attempted no more than 3 times. After a third failed attempt, the blood draw is canceled. After the blood draw, the phlebotomist will remain with the participant until the wound has successfully clotted and/or the participant reports that they feel well enough to resume light activities.

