## **DURATION OF PARTICIPANT PARTICIPATION:**

- This study requires the collection of a tissue sample, which is considered active participation. Study enrollment and the sample collection take about one hour or more to complete depending on the number and types of samples collected. Therefore, active participation will be about one hour and may be up to two hours.
- Inactive participation lasts as long as a participant's samples and data remain at the biobank. There is no limit on the length of time samples and data may be stored. The samples may remain indefinitely at the biobank or until the participant decides to withdraw their participation from the study.

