## 4 STUDY DESIGN

### 4.1 Study Design Rationale

Researchers with institutionally approved study initiatives may request and analyze the biospecimens, genetic material, and health data collected in this study to better understand specific health problems.

The information from this unspecified future biological and biomedical research may facilitate developing new diagnostic tools and personalized treatments for specific health conditions. Such conditions may be acute or chronic, specific or complex, prevalent or rare. Many health conditions overlap with each other clinically and genetically, necessitating in-depth molecular characterization of these conditions to diagnose and treat sufferers of such conditions successfully. Sanguine will facilitate these research endeavors by providing samples of standard quality collected during this study to research institutions.

The biobank may potentially collect biospecimens from rare populations such as elderly participants up to 85 years old. As the American population ages, the Sponsor feels that research on the aging process and conditions and diseases that disproportionately affect the elderly becomes increasingly important.

Other rare and underrepresented populations in research from which the study aims to collect include participants with infectious diseases, including, but not limited to, HIV/AIDS and hepatitis subjects. Because this is a potential population from which biospecimens may come, special training, consideration, and safety will be performed by study staff handling such specimens. Since it is considerably more dangerous to handle specimens with bloodborne pathogens present, many biorepository studies neglect to collect these populations. Unfairly neglected and underrepresented within many biorepository cohorts, the Sanguine's biobank wishes to collect and store quality infectious specimens to help advance biomedical research of such diseases.

The study may require a tissue collection and/or a participant survey for participation. Most tissue collected will come from a blood draw; up to 100mL for the health condition group, 60mL for the exceptive condition group, and up to 180mL for the control group (if determined safe for the participant). Participant surveys may involve participant reported outcomes (PROs) or custom participant surveys.

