Drawing up to 100mL for the health condition group will allow the biobank to collect enough blood from isolating several sub-products from the whole blood, such as serum, plasma, peripheral blood mononuclear cells (PBMCs), and genetic material (DNA/RNA), which are commonly used in biomedical research. A blood draw will provide biological tissue to research and expose participants to minimal risk. A blood draw allows participants flexibility in scheduling the draw, either at a site or in the comfort of their home.

Due to a potential increase of phlebotomy risks for people with certain medical conditions such as cardiovascular diseases, bleeding disorders and late-stage kidney problems, the exceptive condition group will have only up to 60mL drawn to minimize these risks.

The study aims to collect biological tissue from multiple populations to support and advance biomedical research. Drawing a large volume of blood from healthy donors will provide more control biosamples for researchers (posing minimal risk to the participant). Allowing the study efforts to concentrate on collecting samples from various populations to service more research fields.

The control group may have up to 180mL of blood drawn for the study if determined that the participants health will not compromise their safety during the draw. The amount of 180mL is about one-third of the blood drawn during a blood donation and is considered by the Department of Health and Human Safety (HHS) to pose minimal risk to the participant. The study would like to have the potential to draw up to 180mL if the health of the participant allows this amount biological tissue to be collected from one appointment. Since the major risk and discomfort from venipuncture comes from being stuck with the needle, the study believes that a one-time blood draw of a larger volume would be potentially more comfortable for a healthy individual versus undergoing multiple venipunctures.

Participant health will be assessed prior to phlebotomy to determine maximum blood draw volume for all cohorts.

For all research requests that are not covered within this protocol, independent protocol amendments addressing the procedural changes may be drafted to address and minimize possible study risks. A medical practitioner will review the procedural amendments for safety assessment and submit to the IRB for review.

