## **5.2 Participation Criteria**

Eligibility and applicable participant medical history will be overseen by a medical doctor throughout the course of the study to assess participant safety. About 85% of research requests can be completed by the protocol procedures, herein. Some research requests cannot be fulfilled using the procedures discussed below. These requests will be submitted to the IRB as an amendment to this protocol. A medical doctor will review these exceptional collection requests to assess participant safety.

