### **5.3.6 Control Group**

Each participant’s health history will be collected before the blood draw to determine the health and safety of each participant during the venipuncture procedure. The participant’s self-reported medical history is reviewed by trained study staff to assess any medical history that would place a participant at increased risk during a blood collection.

If the participant qualifies for the control group and a researcher has requested the maximum blood volume to be collected, the study staff must assess the health of the participant to determine if they are healthy enough to undergo a 180mL blood draw. The following questions are asked to the participant to assess the safety during the 180mL blood draw:

*Must answer “YES” to all questions in order to be considered for 180mL draw*

1. Is the participant's weight  $\geq 110$ lbs?
2. Is the participant younger than 85 years old?
3. Does the participant have difficulties with blood draws (e.g., hard stick)?

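### For controls aged 85, the 75 mL cap and the 180 mL single-draw screen leave a gap between their age limits

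*Protocol*

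**What the plan says.** Table 1 in Protocol section 5.3.5.1 sets the most blood that may be taken in a 6-week period: 100 mL for the Health Condition group, 60 mL for the Exceptional Condition group and 180 mL for the Control group. The text above the table allows a draw every 7 days, provided the 6-week total stays within these volumes, and allows the whole amount to be taken at once.

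The footnote lowers the limit for some Health Condition and Control participants, namely those "who weigh less than 110 pounds and/or are older than 85 years old will have a maximum collection volume of 75mL" in 6 weeks.

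Section 5.3.6 adds a screen for a single large draw. It applies "If the participant qualifies for the control group and a researcher has requested the maximum blood volume to be collected", and every answer must be yes. Question 1 requires a weight of at least 110 lb. Question 2 is "Is the participant younger than 85 years old".

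Section 5.2.3 admits controls aged 18 to 85 and excludes anyone above 85 on the day of consent. Section 4.1 names "rare populations such as elderly participants up to 85 years old" among those from whom the biobank may collect.

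On individual judgement, section 4.1 states: "Participant health will be assessed prior to phlebotomy to determine maximum blood draw volume for all cohorts". Section 5.2 adds: "Eligibility and applicable participant medical history will be overseen by a medical doctor throughout the course of the study to assess participant safety".

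**The concern.** The footnote and the screen are adjacent safety rules built on the same two characteristics, weight and age. On weight they fit together: below 110 lb the cap applies, and from 110 lb upward question 1 is passed. On age, the cap begins above 85 and the screen stops admitting donors at 85, so neither rule assigns a volume at 85 itself.

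Staff apply these limits draw by draw, and 85 is an age the protocol admits and mentions. At that age one rule treats a control as too old for a 180 mL draw, while the rule beside it does not yet treat the same person as old enough for a reduced limit. What is at stake is a fixed protective number for the oldest eligible controls. The study objective is not affected.

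**Working it through.** The plan gives no calculated figure to reproduce. The check applies the written rules case by case.

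**Inputs**
- 6-week ceilings: Control 180 mL, Health Condition 100 mL (Table 1).
- Cap: weight < 110 lb and/or age > 85 gives at most 75 mL in 6 weeks (Table 1 footnote).
- Screen for a single 180 mL draw, controls only: weight ≥ 110 lb and age < 85, plus a third question (section 5.3.6).
- Eligible age: 18 to 85 at consent (sections 5.2.1 and 5.2.3).
- Minimum interval between draws: 7 days (section 5.3.5.1).

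**Step 1: do the limits meet?**
- Weight: {< 110} and {≥ 110} together cover every weight.
- Age: {> 85} and {< 85} together cover every age except 85.

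**Step 2: outcome for a control weighing at least 110 lb (age in completed years)**

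| Age at draw | Question 2 of the screen | 75 mL cap | Fixed 6-week limit |
|---|---|---|---|
| 84 | passed | does not apply | 180 mL |
| 85 | failed | does not apply | 180 mL |
| 86 or more (repeat draw only) | failed | applies | 75 mL |

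A control below 110 lb is capped at 75 mL by weight at any age, so the gap concerns only those at or above 110 lb.

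**Step 3: what failing the screen prevents.** It prevents one draw of 180 mL. It does not lower the 6-week total. Two draws of 90 mL on days 0 and 7 give 90 + 90 = 180 mL, which equals the Table 1 ceiling, and neither is a 180 mL draw.

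**Step 4: size in volume.** The difference between the limit at 85 and the limit just above it is 180 − 75 = 105 mL in 6 weeks, or 105/180 = 58% of the ceiling. This is a difference between written limits. The volume actually taken is set by individual assessment and may be lower, even below 75 mL.

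**Step 5: when the cap's age condition can operate.** A donor above 85 at consent is excluded. The synopsis describes consent and collection as one session: "Study enrollment and the sample collection take about one hour or more to complete". The age condition therefore cannot apply at the enrolment draw. It can apply only to someone who consents at 85 or younger, passes 85 and gives again. Counting age exactly does not change this, because the exclusion uses the same limit.

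**Step 6: width in age.** In completed years the gap is the whole year of being 85. With exact age it is the 85th birthday, one day. The protocol does not say which convention applies.

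**Step 7: the other cohorts.** A Health Condition donor aged 85 weighing at least 110 lb has a fixed limit of 100 mL, and the 180 mL screen does not concern that group, so no two rules conflict. The Exceptional Condition limit of 60 mL is below 75 mL and outside the footnote.

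**The case against.** The strongest reply is that the two rules were never stated to be complements. One caps a 6-week total and the other gates a single draw. Nothing in the protocol says that failing the screen must lead to a lower fixed number. Question 3, on difficulty with blood draws, can also bar a control from 180 mL and has no fixed fallback either. On this view, refusal followed by individual assessment is simply how the screen works. The cap's starting point above 85 also has a coherent purpose, since repeat draws are allowed and a donor may pass 85 between them.

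Much of this stands. The rules measure different things, the point is limited to their age conditions, and having no effect at enrolment is not in itself a contradiction. What remains is that the same two rules meet exactly on weight and miss by one value on age, at an eligible age, and that the individual assessments set no number. The match on weight suggests a drafting slip, though the documents do not settle which age was meant.

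Two stronger readings are tempting. A reader might infer that controls aged 85 have no volume protection. The documents do not support that: Table 1 still applies, section 4.1 makes the 180 mL conditional on safety and requires an individual maximum, a medical doctor oversees eligibility and history, the phlebotomist checks the donor before the draw, and staff review the history. A reader might also infer that Health Condition donors aged 85 fall into the same gap. They do not, because their 100 mL limit is fixed.

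**Conclusion.** The point holds and is minor. For controls aged 85 weighing at least 110 lb, the protocol refuses a single 180 mL draw but leaves 180 mL per 6 weeks as the only fixed limit, where the reduced limit just above that age is 75 mL. It would be wrong to conclude that these donors are held below 180 mL over 6 weeks, because the screen limits a single draw only.

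The number affected cannot be computed: no age distribution is given, and section 5.1 leaves the number of controls within the 20,000 undetermined. It is probably small. The conclusion rests on a literal reading of both rules. The one-year width assumes that age is counted in completed years, and the statement about enrolment assumes that the first draw follows consent in the same session.

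**What to change.** In the Table 1 footnote, give controls their own age limit: 75 mL per 6 weeks for those who weigh less than 110 lb and/or are aged 85 years or more, with age in completed years on the day of each draw. This matches question 2 of the screen and makes the age condition effective at enrolment. Leave the Health Condition wording as it is, so that those donors keep 100 mL at 85, unless the medical reviewer decides to extend the change. Extending it would lower their limit by 100 − 75 = 25 mL (25%).

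The alternative is to let question 2 admit donors aged 85. That also closes the gap, but controls aged 85 could then be considered for a 180 mL draw, and the cap's age condition would still have no effect at enrolment. No section establishes 75 mL as the medically required limit at 85, so the medical reviewer should confirm the direction.

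The cost is a wording amendment. Controls aged 85 weighing at least 110 lb would give at most 75 mL in 6 weeks instead of an individually set volume of up to 180 mL in total.

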### **5.3 Participant Procedures**

The components of this study include:

1. Participant recruitment
2. Pre-consent Inclusion/Exclusion Screening
  - a. Collection of demographic data
  - b. Collection of self-report health history
3. Cohort Placement
  - a. Health Condition Group
  - b. Exceptional Condition Group
  - c. Control Group
4. Study enrollment and Informed Consent process
5. Biospecimen Collection
  - a. Blood draw by a certified medical professional. Medical history considered.
  - b. Minimal risk biospecimen collection
  - c. Biospecimens that require a clinical procedure and are considered more than minimal risk
    - i. Participant signs procedure-specific ICF
    - ii. Procedures performed by trained medical professionals such as physicians and nurses and at study-approved sites
6. Participant surveys, questionnaires, and PROs
7. Recovery time assessment by the study staff depending on the type of specimen collected, medical history, and health of the individual.
8. Data is securely stored through electronic and physical means.

Please see Appendix C for participant safety workflow.

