#### **5.3.3 Potential Participant Cohort Placement**

After the screening process, trained study staff will review the self-reported medical history to determine cohort placement. If the participant does not report any medical conditions or remarkable medical history, they will be placed in the control cohort. If the participant has reported a medical condition that could potentially increase the presentation of risks associated with phlebotomy, such as bleeding disorders, severe or untreated cardiovascular diseases, late-stage chronic kidney diseases, pregnancy, or splenomegaly, the participant will be placed in the exception condition cohort. This cohort identification is designed to distinguish participants who require additional protection during a phlebotomy procedure. All other participants will be placed

in the health condition group. If a participant does not meet inclusion/exclusion criteria, they will be notified that they cannot participate in this study.

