### **5.3.9 Recovery Time**

Depending on how much blood is drawn, pertinent health history (including current medications), and other tissue donation procedures performed, the phlebotomist and/or study staff will determine how much time a participant will need to recover from the procedure. Steps to recovery include hydration, a snack, and a period of rest before performing strenuous activities or heavy lifting. Phlebotomists will remain with the participant after the phlebotomy procedure to ensure proper clotting and the participant feels well-enough to perform daily activities.

After the visit is completed, Sanguine will send a post-visit survey to the participants for feedback on their experience. Refer to Appendix D for a survey example.

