### 6.3 Protection Against Risks

Physical risks associated with venipuncture will be minimized by utilizing experienced phlebotomists, nurse practitioners, or physicians to draw the blood samples. If the participant suffers a research-related injury, medical expenses will not be covered by the Sponsor. Study participants are not precluded from seeking to collect compensation for injury related to malpractice, fault, or blame on those involved in the research.

All efforts will be made to minimize data-related risks through several levels of protection. First, potential participants are made aware of the potential risks outlined within the ICF during the informed consent process. At the time of potential participant s consent to be contacted either by opting in to the Privacy Policy online or contacting Sanguine directly via email or phone, the participant is given a unique participant identifier, which does not utilize any of his/her direct identifiers (e.g., birth date, zip code, or social security number) as outlined in HIPAA. So, the participant is identified within the study only by this study ID. Biospecimens are processed and stored with sample-specific identification, which is electronically linked to the study ID. Therefore, only necessary study personnel are exposed to the study ID that cannot be connected

with the participant's direct identifiers unless one has administrative access to the linking list portion of the database. Sanguine is guided by the 45 CFR 160 and 164, also known as the Security Rule within HIPAA, to protect participants' privacy and confidential information.

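### The blood-collection procedure lets the phlebotomist leave when either clotting or wellbeing is achieved, while the recovery section calls for both

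*Protocol*

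**What the plan says.** Two sections of the protocol deal with how long the phlebotomist stays after a blood draw.

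- **Section 5.3.5.1, Blood Collection (text under Table 1)** gives the end point of the stay: the phlebotomist remains "until the wound has successfully clotted and/or the participant reports that they feel well enough to resume light activities".
- **Section 5.3.9, Recovery Time** gives the purpose of the stay: phlebotomists remain "to ensure proper clotting and the participant feels well-enough to perform daily activities". It also has the phlebotomist and/or study staff set the recovery time from the volume drawn, the health history and any other procedures. Recovery includes "a period of rest before performing strenuous activities or heavy lifting".

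Other safeguards bear on the same moment:

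- Section 5.3, item 7, lists "Recovery time assessment by the study staff depending on the type of specimen collected, medical history, and health of the individual" as a separate study step.
- The paragraph in 5.3.5.1 that holds the end point also says: "The blood draw appointment follows phlebotomy best practices set forth by" two named bodies.
- Section 6.3 states: "Physical risks associated with venipuncture will be minimized by utilizing experienced phlebotomists, nurse practitioners, or physicians to draw the blood samples".
- Section 4.1 says "the exceptive condition group will have only up to 60mL drawn to minimize these risks".

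Section 5.3.3 explains why the exceptional condition cohort, which includes people with bleeding disorders, is set apart: "This cohort identification is designed to distinguish participants who require additional protection during a phlebotomy procedure".

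**The concern.** The sentence in 5.3.5.1 is an operative safety instruction. It tells the person holding the needle when they may go. Joined by *and/or*, its two conditions become alternatives, so the literal rule is met by a participant who feels well while the wound has not clotted, and by one whose wound has clotted but who still feels faint. Section 5.3.9 treats the conditions as joint, and no visible text says which wording governs.

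The conditions are not substitutes. Section 6.1 names separate physical risks of venipuncture: local effects at the puncture site, and light-headedness or faintness. Meeting one condition says little about the other. Three features of the study make this relevant:

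- The exceptional condition group admits people with bleeding disorders (5.2.2), for whom feeling well is a poor stand-in for clotting.
- Control participants may give up to 180 mL (Table 1), and 5.3.5.1 allows the maximum to be taken at one time. For them, clotting is a poor stand-in for feeling well.
- Collection may take place at home, at work or in another private setting (4.2 and 5.3.5). The protocol does not say that another qualified person will be present once the phlebotomist has left.

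What is at stake is participant safety in a short window after the draw. Data, sample size and analysis are not affected.

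**Working it through.** The plan gives no figure to reproduce here, so the check is a comparison of wording.

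**Step 1: what each section requires.** Let C mean that the wound has clotted and W that the participant feels well enough.

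- 5.3.5.1, with *and/or* in its ordinary inclusive sense: the stay may end when C or W holds.
- 5.3.9, with its purpose clause read as a requirement: the stay may end when C and W both hold.

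**Step 2: all post-draw states.**

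| Clotted (C) | Feels well (W) | 5.3.5.1 alone | 5.3.9 alone | Both applied |
|---|---|---|---|---|
| yes | yes | may leave | may leave | may leave |
| yes | no | may leave | stay | stay |
| no | yes | may leave | stay | stay |
| no | no | stay | stay | stay |
| **States permitting departure** | | **3 of 4** | **1 of 4** | **1 of 4** |

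The difference is 3 − 1 = 2 states: clotted but unwell, and well but not clotted.

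**Step 3: whether another provision closes the gap.** The best-practice reference in 5.3.5.1, the recovery-time assessment in 5.3 (item 7) and 5.3.9, the experienced staff in 6.3 and the 60 mL cap in 4.1 all reduce risk. As far as the text can be read, none of them says that both conditions must be met before departure. Only the closing sentence of that paragraph in 5.3.9 on the phlebotomist's stay does so, and 5.3.5.1 does not refer to it. The content of the cited best practices, the SOPs and the Appendix B safety flow cannot be seen, so nothing is inferred from them in either direction.

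**Step 4: effect of the change.** With *and* in 5.3.5.1, its column becomes the same as that for 5.3.9 (1 of 4), and the two disputed states disappear.

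**What the count does not show.** The four states are not equally likely, and the documents give no frequency for any of them. The 3-against-1 contrast describes how far the rules differ, not how many participants would be affected.

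**A second difference in wording.** 5.3.5.1 speaks of light activities and 5.3.9 of daily activities. The former fits the rest before strenuous effort that 5.3.9 prescribes. This is not part of the finding.

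**The case against.** The strongest reply is that the protocol already contains the safeguard. Section 5.3.9 is the section devoted to recovery, recovery is listed in 5.3 as a step separate from collection, and its sentence covers phlebotomy without exception. The two sections can both be obeyed, and doing so gives the strict result. The loose outcome arises only if staff work from 5.3.5.1 in isolation, and nothing in the document says they do. In addition, *and/or* includes *and*, and leaving a participant whose wound has not clotted is an implausible reading in a paragraph that invokes recognised phlebotomy practice. On this view the point is copy-editing.

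Much of this stands. It is why the point is minor and why no claim is made about actual practice. Two things remain:

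- 5.3.9 states a purpose, whereas 5.3.5.1 states when the stay ends. The only explicit end point in the visible text is therefore the looser one, in the section that describes the draw itself.
- If 5.3.9 is read as no more than a purpose, the formal contrast between the sections softens, but then no visible text firmly requires both conditions. If it is read as a rule, 5.3.5.1 is out of step with it. Either reading supports the same edit.

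**Conclusion.** The point holds, at minor severity. Read literally and alone, 5.3.5.1 permits departure in two post-draw states that 5.3.9 does not. Read together, the sections permit it in one state only, so the practical consequence is limited.

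This rests on two readings: that *and/or* carries its ordinary inclusive meaning, and that the purpose clause in 5.3.9 expresses an intention that both conditions be met. It does not rest on any event rate. No number of affected participants can be given, no harm is alleged, and no statistical quantity in the plan changes. The inconsistency matters most for the exceptional condition group, whose members the protocol itself singles out for extra protection.

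**What to change.** In 5.3.5.1, in the sentence under Table 1 on how long the phlebotomist stays after the draw, replace *and/or* with *and*, and leave the rest of the sentence unchanged. This brings the explicit end point into line with 5.3.9.

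The sponsor may also settle on one activity term for both sections, but that is optional.

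The cost is one conjunction in the next amendment. Visits may run somewhat longer for some participants. The documents do not quantify this, and 5.3.9 already implies it.
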